## 8.6.2 Electrocardiograms

Abnormality criteria to be used in the determination of ECG abnormalities are defined in Table 8–2, where increase and decrease are relative to Baseline values:

Table 8–2: Electrocardiogram Abnormality Criteria		
Parameter	Age Range	Abnormality Criteria
QT interval (ms)	1m-<12y	≥500
	≥12y	≥500 or ≥60ms increase from Baseline
QTc(F) (ms)	<6m	>490, or >15% increase from Baseline
	6m-<17y	>440, or >15% increase from Baseline
	≥17y	≥500 or ≥60ms increase from Baseline
QTc(B) (ms)	<6m	>490, or >15% increase from Baseline
	6m-<17y	>450, or >15% increase from Baseline
	≥17y	≥500 or ≥60ms increase from Baseline
PR interval (ms)	<6m	>150, or ≥25% increase from Baseline
	6m-<3y	>170, or ≥25% increase from Baseline
	3y-<12y	>180, or ≥25% increase from Baseline
	≥12y - <17y	>200, or ≥25% increase from Baseline
	≥17y	Treatment-emergent value >200, >220, >250
QRS interval (ms)	1m-<3y	>90, or ≥25% increase from Baseline
	3y-<12y	>100, or ≥25% increase from Baseline
	≥12y - <17y	≥110, or ≥25% increase from Baseline
	≥17y	Treatment-emergent value >100, >120, >140
Heart rate (bpm)	<6m	<100, >180

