16. Subject has sick sinus syndrome without a pacemaker, or second- or third-degree atrioventricular (AV) block.
17. Subject has a clinically relevant ECG abnormality, in the opinion of the principal investigator (ie, second- or third-degree heart block or a corrected QT interval [QTc] greater than 450ms).
18. Subject has hemodynamically significant heart disease (eg, heart failure).
19. Subject has an arrhythmic heart condition requiring medical therapy.
20. Subject has a known cardiac sodium channelopathy, such as Brugada syndrome.
21. Female subject who is pregnant or nursing, and/or a female subject of childbearing potential who is not surgically sterile or does not practice 1 highly effective method of contraception (according to International Conference on Harmonisation [ICH] guidance defined as those that result in a failure rate of less than 1% per year when used consistently and correctly), unless sexually abstinent, for the duration of the study. Female subject of childbearing potential taking enzyme inducing antiepileptic drugs (EI AEDs) (carbamazepine, phenytoin, barbiturates, primidone, topiramate, oxcarbazepine) who is not surgically sterile or does not practice 1 highly effective method of contraception according to the World Health Organization recommendation (ie, depot medroxyprogesterone acetate, norethisterone enantate, intrauterine devices, combined injectables, and progestogen implants) with administration of EI-AEDs or does not practice 2 combined methods of contraception (ie, combined hormonal contraception plus

barrier method with spermicidal agent), unless sexually abstinent, for the duration of the study.

22. Subject has been treated with vigabatrin and experienced any vision loss. Subjects who have received vigabatrin in the past must have documentation of an assessment for vision loss prior to study entry or documentation of why visual field testing cannot be performed.
23. Subject has been treated with felbamate and has experienced any serious toxicity issues (defined as liver failure, aplastic anemia) with this treatment. Subjects treated with felbamate for less than 12 months are excluded. Note: any subject who has been treated with felbamate for at least 12 months and has not experienced serious toxicity issues is eligible.
24. Subject is taking monoamine oxidase (MAO) inhibitors or narcotic analgesics.

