6.3 Withdrawal criteria

Subjects are free to withdraw from the study at any time, without prejudice to their continued care.

All subjects who withdraw from the study due to an AE must be followed until resolution of the event or until the event is considered stable.

Subjects **must** be withdrawn from the study if any of the following events occur:

1. Subject experiences intolerable AEs, including clinically relevant abnormal laboratory findings that, in the opinion of the investigator, preclude further participation in the study.
2. The sponsor or a regulatory agency requests withdrawal of the subject.
3. Female subject achieves menarche and does not practice contraception as provided in Exclusion Criterion 21, unless sexually abstinent.
4. Subject becomes pregnant, as evidenced by a positive pregnancy test.
5. Subject has QTc interval of ≥ 500 ms that is confirmed by a cardiologist overread on any ECG.
6. Subject develops second- or third-degree AV block.
7. Subject is unwilling or unable to continue, or the parent/legal representative is unwilling or unable to allow the subject to continue in the study.
8. Investigator decides that withdrawal from further participation would be in the subject's best interest.
9. Subject has a prolongation or worsening of overall seizure duration, frequency, type, or pattern considered by the investigator as serious enough to warrant discontinuation from the study.

10. Subject uses rescue medication in excess of that permitted by the protocol.
11. Subject needs any alteration in AED daily dose or VNS settings.
12. In the case of liver function test (LFT) results of transaminases (AST, ALT, or both) $\geq 3x$ ULN to $< 5x$ ULN and total bilirubin $\geq 2x$ ULN or transaminases (AST, ALT, or both) $\geq 5x$ ULN, LCM must be immediately discontinued and the subject withdrawn from the study. The LFTs will be repeated as soon as possible, and in no case > 1 week later.
13. For subjects ≥ 6 years of age, subject has actual suicidal ideation as indicated by a positive response ("Yes") to either Question 4 or Question 5 of the "Since Last Visit" version of the C-SSRS. The subject should be referred immediately to a Mental Healthcare Professional and must be withdrawn from the study.

Subjects **may** be withdrawn from the study if any of the following events occur:

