11.7 Other safety measurements

11.7.1 Seizure frequency

See Section 9.1.

11.7.2 24-hour ambulatory EEG

Subjects will be asked to return to the clinic on the morning of the day prior to Visit 2, Visit 6, and Visit 9/Early Termination to begin 24-hour ambulatory EEG recordings for evaluation of spike-wave discharges.

11.7.3 12-lead ECG

Standard 12-lead ECGs will be performed according to the tabular schedule of study procedures in Section 5.2. Two interpretable recordings approximately 20 to 30 minutes apart are required. At Visit 2, Visit 6, and Visit 9/Early Termination, the 12-lead ECG recordings should be performed at least 15 minutes after removal of scalp electrodes used for the 24-hour ambulatory EEG recording and prior to blood sample collection. At all other visits, 2 recordings will be performed prior to blood sample collection and measurement of vital signs.

Care should be taken to assure proper lead placement and quality ECG recordings. Subjects should rest in the supine position for approximately 5 minutes before the ECG recordings and during the recordings, if possible.

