**Table 8–2: Electrocardiogram Abnormality Criteria**

Parameter	Age Range	Abnormality Criteria
	6m-<3y	<90, >130
	3y-<12y	<60, >130
	>12y	<50, >120

bpm=beats per minute; m=months; ms=milliseconds; QTc=corrected QT interval; y=years.  
A month is defined as 30 days; a year is defined as 365.25 days.

Treatment-emergent ECG abnormalities are defined as values meeting the criteria given in Table 8–2 at any post-Baseline visit during the Treatment Period (including unscheduled visits) and not meeting the same criteria during Baseline.

For ECGs, baseline will be defined as the average of all pre-dose interpretable readings. For all post-baseline visits, the average of all interpretable readings at the specified visit will be used for summaries.

Observed results and changes from Baseline in ECG results will be summarized for all visits and the Last Visit.

The number and percentage of subjects with no abnormality, an abnormal but not clinically significant finding, and a clinically significant finding, will be summarized by visit, including last visit. Percentages will be relative to the number of subjects with an ECG assessment at the respective visit. Subjects are counted once at each visit based on the worst observed outcome across all abnormalities reported at that visit.

Summaries of shifts from Baseline to post-Baseline visits (including Last Visit) will also be provided based on the categories normal, abnormal, not clinically significant, and abnormal, clinically significant.

The number and percentage of subjects with treatment-emergent ECG abnormalities will be presented by visit and treatment group. Abnormalities reported at an unscheduled visit will be summarized under the scheduled visit preceding the unscheduled visit (if the abnormality was not present already at the preceding scheduled visit). Percentages will be based on the number of nonmissing values for the variable and visit. In addition, a listing including all ECG parameter values for subjects meeting any abnormality criteria will be provided.

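### The QTc(F) row for ages 6 months to under 17 years has no 500 ms tier, so if the entry limit is read as Fridericia an eligible child can reach the withdrawal limit uncounted as treatment-emergent

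*SAP*

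**What the plan says.** **SAP 8.6.2, Table 8-2.** From 6 months to under 17 years the QTc(F) criterion is ">440, or >15% increase from Baseline" and the QTc(B) criterion is ">450, or >15% increase from Baseline". From 17 years both rows read "≥500 or ≥60ms increase from Baseline". Under 6 months the absolute limit is 490 ms. Uncorrected QT has a 500 ms limit at all ages and, from 12 years, a 60 ms rise limit as well.

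**SAP 8.6.2, text.** A treatment-emergent abnormality meets a Table 8-2 criterion during the Treatment Period "and not meeting the same criteria during Baseline". The ECG Baseline is the mean of all interpretable pre-dose readings. After Baseline, "the average of all interpretable readings at the specified visit will be used for summaries".

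**Protocol 6.2, exclusion 17.** The child is excluded for an ECG abnormality that the investigator judges clinically relevant, including "a corrected QT interval [QTc] greater than 450ms".

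**Protocol 6.3, withdrawal criterion 5.** The child must be withdrawn for a QTc of 500 ms or more "that is confirmed by a cardiologist overread on any ECG". Neither protocol criterion names a correction formula.

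**Protocol 11.7.3.** "Two interpretable recordings approximately 20 to 30 minutes apart are required".

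**The concern.** The entry limit (450 ms) lies above the QTc(F) abnormality limit for this age band (440 ms). A child who enters between the two already meets the absolute criterion at Baseline, so only the relative criterion is left to detect a later change. If that criterion needs a value above 500 ms to fire, the treatment-emergent table cannot see the point at which the protocol itself stops treatment. A 17-year-old with the same tracings would be counted. The age band matters because most of the planned sample falls in it: about 40 of 50 subjects are to be 4 to under 18 years, and all of those except the 17-year-olds use these rows.

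**Working it through.** The plan states no figure to reproduce. The check applies the Table 8-2 limits and the treatment-emergent rule directly.

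**Inputs.** The limits quoted above, plus the standard relations at heart rate HR: QTcB = QTcF × (HR/60)^(1/6) and QT = QTcF × (60/HR)^(1/3). Heart rates are my assumption; the documents give none.

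**Step 1: QTc(F) row.** With Baseline QTcF at 441 to 450, the >440 criterion is already met. For the >15% criterion:

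| Baseline QTcF | Rise at 500 ms | 15% line (1.15 × Baseline) |
|---|---|---|
| 441 | 500/441 − 1 = 13.4% | 507.2 |
| 445 | 500/445 − 1 = 12.4% | 511.8 |
| 450 | 500/450 − 1 = 11.1% | 517.5 |

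So the row does not count a visit value of 500, and stays silent up to about 507 to 517 ms. If the Baseline comparison is made on the whole row, it never fires for this child. The gap exists under either reading of the rule.

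**Step 2: QTc(B) row.** Baseline QTcB exceeds 450 when HR > 60 × (450/QTcF)^6. That is 67.7 bpm at QTcF 441, 64.2 at 445 and 60.0 at 450. Above those rates the >450 criterion is already met. At an unchanged rate the percentage rise in QTcB equals that in QTcF (11% to 13%), so the >15% criterion fails too. At or below those rates this row does count the child.

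**Step 3: QT row.** At an unchanged rate above 60 bpm, QT stays below 500 when QTcF is 500. The largest rise in the band is from 441 to 500 at 68 bpm: QT goes from 423.0 to 479.6, a rise of 56.6 ms, below 60.

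**Worked case, 80 bpm at both visits.** QTcF 445 to 500 (+12.4%); QTcB 467 to 525 (already above 450, +12.4%); QT 404 to 454 (below 500, +50 ms). No QT or QTc row is newly met.

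**How far the rate may move.** From Baseline QTcF 445 at 80 bpm, with criteria judged separately, QTcF 500 goes uncounted at on-treatment rates of 75 to 91 bpm (12 to under 17 years) or 61 to 91 bpm (6 months to under 12 years). Below the window a QT criterion fires; above it QTcB rises by more than 15%.

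**Other ages.** Under 6 months, 500 exceeds 490 and an eligible Baseline does not. From 17 years, 500 is itself the criterion. Neither group has the gap.

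**Check of the remedy.** With a separate 500 ms criterion, every child entering at 441 to 450 is counted at 500, because Baseline is below 500. A 60 ms rise criterion alone would not do it: it first fires at 441 + 60 = 501 up to 450 + 60 = 510.

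**The case against.** The strongest reply is that several conditions must coincide and that the safety report does not lose the child.

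- **Formula.** If exclusion 17 is applied as Bazett, Baseline QTcB is at most about 450 and a later QTcB of 500 is counted. The gap needs a Fridericia reading, which the protocol allows but does not state.
- **Entry.** Two recordings are taken at each of Visits 1 and 2. If exclusion 17 acts on each reading, all four must be at or below 450 and still average above 440. The investigator must also accept a Bazett value already above 450 (467 in the worked case).
- **Other outputs.** The child is in the listing of subjects meeting any ECG criterion, in the observed and change-from-Baseline summaries (whose statistics include the maximum, SAP 3.1) and in disposition. SAP 8.6.2 also plans a by-visit count of clinically significant findings on the worst outcome, and shift tables. A QTc that forces withdrawal would ordinarily be rated clinically significant, though Protocol 11.7.3.1 leaves that to the investigator. If it is reported as an adverse event, it enters the adverse event tables too.

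All of this stands. It limits the size of the problem but does not make the count right.

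A reader might also infer that averaging the visit's readings is a second defect, because withdrawal acts on any ECG. Readings of 502 and 490 average 496, and the child could be withdrawn. But with Baseline QTcF at or below 440, 496 is already counted by the >440 criterion. Averaging therefore adds nothing to the present count outside the same narrow band; it is a question of tracing withdrawals.

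**Conclusion.** The point holds as a minor one. Assume that the entry limit is read as Fridericia, mean pre-dose QTcF is 441 to 450, Baseline heart rate is above about 60 to 68 bpm, and the rate on treatment is similar. A child aged 6 months to under 17 years can then reach QTcF 500 and be treatment-emergent in no QT or QTc row.

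One such child is 1/50 = 2 percentage points of the planned sample. The documents give no frequency, and the conditions suggest that it is rare. ECG is one of the other safety variables in a descriptive study; neither primary variable nor any withdrawal decision changes.

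Two stronger readings are tempting. One is that any child entering at 441 to 450 goes uncounted at 500: this fails at lower heart rates, at rates that shift enough, and under Bazett. The other is that the report would show no sign of a child withdrawn for QTc: the listing, interval summaries and disposition rule that out.

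**What to change.** 1. In SAP Table 8-2, QTc(F) row, 6 months to under 17 years only, add ≥500 ms as a separate criterion.
2. In SAP 8.6.2, state that for this row the ≥500 ms criterion is compared with Baseline on its own: it is treatment-emergent if Baseline QTcF was below 500 ms. Keep the visit average, as the SAP already does.
3. Optionally, list any single reading of 500 ms or more, so that a withdrawal under criterion 5 can be traced when the visit average is lower.

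The cost is one table entry and one sentence, plus a listing if wanted. There is no protocol change, new measurement or moved limit.

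The change should stay this narrow. A 500 ms tier in the QTc(B) row is not needed to close the gap and would add counts driven by heart rate alone: with QTcF unchanged at 450, a rate going from 100 to 114 bpm takes QTcB from 490 to 501. A general rule that every criterion is judged separately would also reach the PR and QRS rows. A highest-single-reading rule for every 500 ms QTc criterion would alter the rows from 17 years.

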**Table 8–2: Electrocardiogram Abnormality Criteria**

Parameter	Age Range	Abnormality Criteria
	6m-<3y	<90, >130
	3y-<12y	<60, >130
	>12y	<50, >120

bpm=beats per minute; m=months; ms=milliseconds; QTc=corrected QT interval; y=years.  
A month is defined as 30 days; a year is defined as 365.25 days.

Treatment-emergent ECG abnormalities are defined as values meeting the criteria given in Table 8–2 at any post-Baseline visit during the Treatment Period (including unscheduled visits) and not meeting the same criteria during Baseline.

For ECGs, baseline will be defined as the average of all pre-dose interpretable readings. For all post-baseline visits, the average of all interpretable readings at the specified visit will be used for summaries.

Observed results and changes from Baseline in ECG results will be summarized for all visits and the Last Visit.

The number and percentage of subjects with no abnormality, an abnormal but not clinically significant finding, and a clinically significant finding, will be summarized by visit, including last visit. Percentages will be relative to the number of subjects with an ECG assessment at the respective visit. Subjects are counted once at each visit based on the worst observed outcome across all abnormalities reported at that visit.

Summaries of shifts from Baseline to post-Baseline visits (including Last Visit) will also be provided based on the categories normal, abnormal, not clinically significant, and abnormal, clinically significant.

The number and percentage of subjects with treatment-emergent ECG abnormalities will be presented by visit and treatment group. Abnormalities reported at an unscheduled visit will be summarized under the scheduled visit preceding the unscheduled visit (if the abnormality was not present already at the preceding scheduled visit). Percentages will be based on the number of nonmissing values for the variable and visit. In addition, a listing including all ECG parameter values for subjects meeting any abnormality criteria will be provided.

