Table 5-1: Schedule of study assessments (Baseline Period, Titration Period, Maintenance Period, Taper Period, End of Study Period and Unscheduled Visit)

Assessments	Baseline Period (6 weeks)		Treatment (18 weeks)												End of Study Period		Unscheduled Visit ^a			
	Titration Period (6 weeks)						Maintenance Period (12 weeks)													
Visit	V1	TC 1	V2	TC 2	V3	TC 3	V4 ^c	V5 ^c	End of Titration V6	TC 4	V7	TC 5	V8	TC 6	V9/ET ^d	TC 7 ^e	End of Taper Visit ^f	Safety FU Visit ^g	Safety FU TC ^g	At any time
Week in study	-6	-3	Day 1	1	2	3	4	5	6	8	10	12	14	16	18	19	20-22	22-24	24-26	

the study. The PedsQL will be used only in countries where a translated version is available.

^w At the end of Visit 2, subjects should take the first dose of LCM in the clinic.

^x For subjects entering Taper Period and not entering SP848.

^y The subject diary will be dispensed at Visit 1. At all subsequent visits, the subject and/or legal representative(s) will be reminded to complete the diary on a daily basis.

^z As applicable, VNS assessment will only be performed for subjects with an implanted VNS device at Visit 1.

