8.2 Titration Period

8.2.1 Visit 2 (Day 1)

Subjects will be asked to return to the clinic on the morning of the day prior to Visit 2 (end of Week 0) to begin 24-hour ambulatory EEG recordings. Scalp electrodes will be attached, and subjects will receive a recording device. Subjects will be asked to return approximately

24 hours later (for Visit 2, Day 1) for removal of the scalp electrodes and return of the recording device. At Visit 2, the investigator should determine whether the subject is still eligible and willing to continue in the study.

The following will be performed prior to the first dose of LCM:

- Review inclusion/exclusion criteria.
- Concomitant AED(s) assessment.
- VNS assessment (for subjects with an implanted VNS device).
- Concomitant medication(s) assessment.
- Complete physical examination.
- Complete neurological examination.
- 12-lead ECG (2 interpretable recordings [20 to 30 minutes apart] to be performed prior to any blood draws and vital signs assessment and, if possible, with the subject in the supine position for approximately 5 minutes preceding the recordings and during the recordings. Recordings should be performed at least 15 minutes after removal of scalp electrodes used for the 24-hour ambulatory EEG recording).
- Vital signs (BP and pulse rate, including orthostatic assessments in ambulatory subjects).
- Body weight and height assessment.
- C-SSRS (if applicable).
- Blood sample for clinical chemistry and hematology.
- Blood sample for LCM and concomitant AED plasma concentrations (before dosing with LCM). Blood sample will be drawn along with clinical chemistry and hematology samples.
- Achenbach CBCL (if applicable); CBCL/1½-5 or CBCL/6-18 for pediatric subjects ≥18 months of age.
- Bayley Scales of Infant and Toddler Development®, Third Edition (Bayley-III Scales) (if applicable). For pediatric subjects <18 months of age at Baseline enrolled in English-speaking countries.
- BRIEF-P (≥2 years to <5 years of age)/BRIEF (≥5 years of age) (version consistent with age at the visit).
- PedsQL for subjects ≥1 month to ≤18 years of age (version consistent with age at the visit).
- Urine sample for urinalysis (if applicable).
- Urine pregnancy test (if applicable).
- Subject diary return/review.
- AE reporting.

- Review withdrawal criteria.
- Contact IXRS.
- Dispense subject diary.
- Reminder to complete subject diary on a daily basis.
- Health care resource use.

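### Treatment-emergent ECG abnormalities from unscheduled visits before Visit 3 would be tabulated at Visit 2, a pre-dose Baseline visit

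*SAP*

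**What the plan says.** SAP Section 8.6.2 counts an ECG abnormality as treatment-emergent if it meets the criteria of the ECG abnormality table "at any post-Baseline visit during the Treatment Period (including unscheduled visits) and not meeting the same criteria during Baseline". On the reference value it says: "For ECGs, baseline will be defined as the average of all pre-dose interpretable readings".

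The number and percentage of subjects with such abnormalities are presented by visit. For unscheduled visits the rule is: "Abnormalities reported at an unscheduled visit will be summarized under the scheduled visit preceding the unscheduled visit". One condition follows: the rule applies "if the abnormality was not present already at the preceding scheduled visit". On the denominator: "Percentages will be based on the number of nonmissing values for the variable and visit". The section also promises a listing of all ECG parameter values for every subject who meets any criterion.

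In Protocol Section 8.2.1 the Visit 2 procedures, the 12-lead ECG among them, stand under the line "The following will be performed prior to the first dose of LCM". A footnote to Protocol Table 5-1 adds: "At the end of Visit 2, subjects should take the first dose of LCM in the clinic".

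The next scheduled ECG is at Visit 3, at the end of Week 2 with a window of 2 days either side (Protocol Section 8.2.3). The only scheduled contact in between is the Week 1 telephone call, which has no ECG (Protocol Section 8.2.2). Unscheduled visits may take place at any time after Visit 1, with an ECG at the investigator's judgment (Protocol Section 8.5).

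**The concern.** The rule carries every unscheduled finding back to an earlier visit. For most of the study that visit is itself on treatment, so the row label is only imprecise. Between the first dose and Visit 3 the earlier visit is Visit 2, where no child has yet taken lacosamide and where the ECG feeds the Baseline average. An on-treatment PR, QRS or QTc abnormality would then appear in a pre-dose row.

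A reader of the table could take it for a pre-treatment finding, and would not see it in the Week 2 row. The rows cannot be added up to repair this, because a child who is abnormal at several visits is counted in each of them. The table has no row giving the number of children with an abnormality at any on-treatment ECG, so the simplest safety count has to be worked out from the listing.

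**Working it through.** The plan states no figure on this point, so there is none to reproduce. The check applies the SAP rule to the protocol's ECG schedule.

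**Inputs**
- Visit 2 is Day 1; its ECG is pre-dose and the first dose comes at the end of the visit (Protocol Section 8.2.1 and Table 5-1).
- Scheduled clinic visits with an ECG from then on: Visit 2, Visit 3 (Week 2), Visits 4 and 5 (Weeks 4 and 5, both optional), Visit 6 (Week 6), Visit 7 (Week 10), Visit 8 (Week 14) and Visit 9 (Week 18).
- Day convention (mine; the documents give none): end of Week w = Day 7w + 1. Visit 3 is then Day 7 × 2 + 1 = 15, and Visit 6 is Day 7 × 6 + 1 = 43.

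**Step 1: which days map to Visit 2.** An unscheduled ECG maps to Visit 2 if it falls after Day 1 and before the actual Visit 3.

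| Visit 3 held on | Days mapped to Visit 2 | Number of days |
|---|---|---|
| Day 15 − 2 = 13 | 2 to 12 | 11 |
| Day 15 | 2 to 14 | 13 |
| Day 15 + 2 = 17 | 2 to 16 | 15 |

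A post-dose unscheduled ECG later on Day 1 would go the same way.

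**Step 2: does the condition in the rule prevent this?** It withholds the assignment only if the abnormality was already present at Visit 2. A treatment-emergent finding must be absent at Baseline, so the condition can apply only where the Visit 2 reading alone met the criterion and the average of all pre-dose readings did not. That should be rare.

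**Step 3: the denominator.** At Visit 2 the nonmissing values are pre-dose ECGs. The numerator would be on-treatment findings and the denominator pre-treatment recordings.

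**Step 4: consistency with the definition.** Treatment-emergent requires a post-Baseline visit. Visit 2 contributes to Baseline. No sentence exempts Visit 2 from the rule or sends these findings to another row.

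**Step 5: scale.** One child among the planned 50 is 1/50 = 2 percentage points. Summaries are also split by age group (SAP Section 3.1). The group under 4 years is planned at 10 or more children, so there one child is at most 1/10 = 10 points if exactly 10 or more have a value. These figures show the weight of a single event and are not a forecast.

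**The case against.** The strongest reply is that this is a labelling flaw in one descriptive table, and most of that stands.

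- **A reader might infer that the events are lost.** The documents do not support this. The rule says they are summarized, the definition includes unscheduled visits, and the listing shows all ECG values for affected children.
- **A reader might infer that serious conduction events would go unseen.** They have other routes. Second- and third-degree AV block, other named arrhythmias and marked bradycardia are adverse events of special interest (Protocol Section 11.3). As adverse events they enter the TEAE tables, which include separate Titration and Maintenance summaries (SAP Section 8.2.2), and the preferred terms in SAP Appendix 13.1 have their own table. None of this depends on ECG visit mapping. ECGs at early termination are also unaffected, because SAP Section 4.2.1 maps them forward.
- **A reader might infer that backward mapping assigns events to the wrong dose.** Summaries are generally not split by dose (SAP Section 3.6). Dose is fixed in Maintenance, and holds and back-titration are allowed in Titration, so an earlier visit need not mean a lower dose.
- **A reader might want all unscheduled ECGs mapped forward.** That can misplace events the other way: if Visits 4 and 5 are not held, a Week 3 finding would be filed at Week 6. After Visit 3 the direction is a matter of preference.
- **A reader might quote the affected days as a share of the 18 treatment weeks.** That is a share of calendar time, not of events.

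What the reply does not remove is the Visit 2 assignment itself, which follows from the text as written, and the absence of an any-time row. The Last Visit row in other ECG summaries considers unscheduled assessments but reports only the last value.

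**Conclusion.** The point holds, and it is minor. As written, the SAP would place on-treatment ECG abnormalities found before Visit 3 in a pre-dose row over a pre-dose denominator, against its own definition. The interval is nominally Days 2 to 14 and ends between Day 12 and Day 16 depending on when Visit 3 is held. A different day-counting convention could move these limits by a day without changing the conclusion.

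The conclusion rests on taking the rule literally and on reading the preceding scheduled visit as a clinic visit. Counting the Week 1 telephone contact as a visit would not help, since no ECG is done there and the row would have no denominator. The number of events affected is unknown because the documents give no expected rate of unscheduled ECGs. No decision rule in the plan uses this table.

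**What to change.** Two changes to SAP Section 8.6.2:

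1. Add a sentence stating that abnormalities from post-dose unscheduled ECGs are never assigned to Visit 2. Those found before Visit 3 go either to Visit 3 or to a separate post-Baseline unscheduled row. The separate row avoids counting a child at Visit 3 who has no Visit 3 ECG.
2. Add a table row, *Any post-dose ECG in the Treatment Period (scheduled or unscheduled)*, counting each child once. The denominator is children with at least 1 post-dose ECG value for the variable.

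The mapping of later unscheduled visits can stay as it is. The added row follows the SAP's own practice: laboratory summaries take unscheduled values into the post-Baseline minimum and maximum (SAP Section 8.5), and the physical and neurological examinations have a shift to any post-Baseline finding (SAP Section 8.6.3). The cost is one sentence and one table row, with no new data.
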